A Prospective Randomized Control Trial of The Effectiveness of Alvimopan as a Rescue Treatment of Postoperative Ileus Following Colorectal Surgery

Principal Investigators:

[name]

[name]

Co-investigator:

[name]

[name], PA

Biostatistician:

[name]

Protocol Version: 10/25/21

NCT04405037

Background:

Most patients who undergo colorectal or small bowel resection (about 350,000 patients/year in the United States) will experience postoperative ileus, a temporary impairment of gastrointestinal function (8). POI is associated with increased morbidity, increased hospital length of stay (LOS), and increased health care costs (13). In most patients, LOS is typically determined by timing of GI recovery and POI has been shown to increase LOS by an average of 6 days with an annual cost of \$1.46 billion (8). Currently, there is no specific treatment for or prevention of POI (8,16). Alvimopan is an oral, peripherally acting selective mu-opioid receptor antagonist that has been studied in patients undergoing abdominal and pelvic surgery, and was FDA approved in 2008 for short-term use to accelerate upper and lower gastrointestinal recovery in inpatients following segmental large or small bowel resection with primary anastomosis (8,14,15,16). Studies have demonstrated the effectiveness of Alvimopan in reducing time to return of bowel function, LOS and cost in abdominal surgery, however there have also been conflicting findings that have not observed these benefits in laparoscopic colorectal surgeries, have found no reduction in readmission rates or an increase in readmission rates, or have not found a reduction in cost (14,13,16,17,18). It is possible that the use of Alvimopan may be more effective in some populations than in others (i.e. low risk vs. high risk for POI, open vs. laparoscopic surgery) (13). The high cost of Alvimopan (currently \$142.32/capsule) is of significant concern, and given prophylactically to all patients undergoing colorectal or small bowel resection may not be economically prudent as not all patients will develop POI or require treatment for POI (mild cases). This study aims to evaluate the cost effectiveness of Alvimopan as rescue therapy in patients undergoing colorectal or small bowel resection who develop POI, and its safety and effectiveness in reducing LOS and POI duration.

Hypothesis:

We hypothesize that the use of alvimopan as rescue therapy in patients undergoing colorectal and small bowel resection surgery who develop POI can shorten their duration of POI and hospital length of stay.

Objectives:

To perform a prospective RCT to evaluate the effect of alvimopan as rescue therapy compared to standard of care in reducing the duration of post-operative ileus and post-operative LOS after colorectal and small bowel resection surgery.

Protocol:

This will be a prospective randomized control trial with a total of 58 patients, 29 in each group. Patients who undergo laparoscopic or open colorectal resection, small bowel resection, or ileostomy reversal with small bowel resection that subsequently develop postoperative ileus will be eligible for enrollment. If they meet inclusion/exclusion criteria, they will be randomized at the time of diagnosis of postoperative ileus to receive Alvimopan as rescue therapy or to receive conservative standard care.

At the time of diagnosis of postoperative ileus and after enrollment and randomization, all patients will be returned to NPO status. Nasogastric tubes (NGT) may be placed for gastric decompression at the discretion of the surgical team if clinically indicated. In the event that an NGT is placed, medications will be given orally or via the NGT, which will be clamped for 30 minutes after administration. Patients will continue on standard ERAS pathways with the exception of reduction of diet. Antiemetics will be given as clinically indicated; however, no prokinetic or promotility agents will be given as scheduled dosages.

Patients randomized to the study group will be given a maximum of 3 doses of Alvimopan 12mg orally, 12 hours apart. Alvimopan will be given from the time of diagnosis of postoperative ileus to the time of return of bowel function or the maximum 3 doses. Subsequent Alvimopan doses will be given if there is no return of bowel function or if symptoms of distension and/or nausea persist despite some return of bowel function.

All patients will follow a standard ERAS pathway after surgery, with early feeding and ambulation, along with opioid minimizing measures as is our standard postoperative protocol.

The patient and surgical team will be able to know which arm of the study the patient is in based on documentation in the medical record of the administration of Alvimopan.

Standard discharge criteria will be applied to all patients, including: Passage of stool, Ability to tolerate solid food and to drink comfortably, Adequate oral analgesia, Patient's willingness to be discharged.

Study Design:

This will be a prospective randomized control trial. Patients who undergo laparoscopic or open colorectal resection, small bowel resection, or ileostomy reversal with small bowel resection that subsequently develop postoperative ileus will be eligible for enrollment.

If they meet inclusion/exclusion criteria, they will be randomized at the time of diagnosis of postoperative ileus to receive Alvimopan as rescue therapy or to receive conservative standard care.

Alvimopan will be prescribed as 1 dose PO with clamping of any NG tube if present for 30 minutes. A subsequent dose (up to a maximum of 3 doses) may be repeated 12 hours later if there has been no recovery of GI function.

Outcome: The primary outcome measure will be hospital length of stay after the diagnosis of POI (date of diagnosis until actual discharge). The secondary outcome measures will be: time to return of bowel function (date and time ileus identified to date and time of passing flatus, stool and tolerating diet), complications (serious adverse events and adverse events of interest 30 days postoperatively), number of re-operations (any reoperations within 30 days of surgery), number of readmissions (any readmissions within 30 days of surgery)

Inclusion Criteria:

1. Subjects who have benign or malignant colonic or rectal disease that have undergone laparoscopic or open colorectal resection, small bowel resection or ileostomy reversal with small bowel resection and subsequently developed postoperative ileus, defined as:
 - a. Patients with symptoms of bloating with or without nausea and vomiting, who require either:
 - i. Return to NPO status after initial diet attempts
 - ii. Undergo placement of a nasogastric tube
 - b. Patients with absence of passage of flatus or stool who are either
 - i. More than 5 days after open surgery without recovery of GI function
 - ii. More than 3 days after laparoscopic surgery or ileostomy closure without recovery of GI function
2. Subjects who are 18 years of age and older
3. Subjects of either gender
4. Subjects who are willing and able to adhere to protocol requirements, agree to participate in the study program and provide written and informed consent.

Exclusion Criteria:

1. Subjects who received Alvimopan preoperatively.
2. Subjects that have already received scheduled peripherally acting mu-opioid receptor antagonists postoperatively.
3. Subjects that have taken therapeutic doses of opioids for more than 7 days immediately prior to surgery.

4. Subjects with severe hepatic impairment.
5. Subjects with end-stage renal disease.
6. Subjects who are pregnant.
7. Subjects who have undergone imaging suggesting a small bowel obstruction.
7. Subjects with a medical condition that may interfere with the use of the study medication Alvimopan.
8. Subjects who have a condition or general disability or infirmity that in the opinion of the investigator precludes further participation in the study

Data to be collected:

The medical/surgical information below will be collected as part of this research study and is all information already available as part of the patients medical chart.

A) Preoperative variables:

1. Patient name, medical record number
2. Past Medical History
3. Past Surgical history
4. Preoperative Medications (including steroids, anticoagulation, opioid use)
5. Pre-operative Diagnosis
6. Patient Demographics (age, gender, BMI, ASA score)

B) Intraoperative variables:

1. Procedure performed
1. Time of surgery
2. Wound classification
3. Estimated blood loss
4. Intraoperative transfusion
5. Intraoperative IV fluids given
6. Conversion from laparoscopic to open procedure

7. Stoma creation

C) Postoperative variables:

1. Time/day of diagnosis of ileus
2. Abdominal imaging demonstrating ileus if present
3. Time from surgery to medication given
4. Time from ileus diagnosis to medication given
5. Was there return of bowel function (flatus or stool, solid or liquid, stoma output) prior to ileus
6. Intra-abdominal infection/anastomotic leak
7. Time/day of return of bowel function post ileus (flatus and stool- solid or liquid, and stoma function)
8. Time/day of ability to tolerate oral diet (liquid and solid food)
9. Nasogastric tube placement and daily output
10. Duration of nasogastric tube
11. Use and type of anti-emetics given
12. Total number of Alvimopan doses given
13. Post operative complications including reoperation
14. Length of stay in hospital, defined as time from surgery to discharge
15. Length of POI, defined as time from diagnosis of POI until discharge
16. 30-day readmissions

Study Completion of participation in the study will be 30 days after the date of POI. Any readmission up to 30 days post-operatively to the hospital as a direct result of their surgery will be followed. The patients will follow-up with the surgeon in the office in approximately 3-6 weeks, which is considered standard of care for all patients undergoing colorectal surgery and is not considered part of the research study. Any patient for whom follow-up documentation is missing or incomplete shall be contacted via telephone. The purpose of the call will be to simply determine return to function and outcome. Only a co-investigator shall contact the subject and will identify themselves at the beginning of the call. Any subject can reserve the right not to participate in the phone call interview; they would remain in the study.

Statistical Analysis

Planned Data Analysis:

Descriptive statistics will be computed for all variables including mean \pm standard deviation or median [25th, 75th percentiles] for continuous factors and frequency (percent) for categorical variables.

Univariate analyses will be conducted to compare the distribution of pre-op characteristics across treatment groups using t-test or Wilcoxon rank sum tests for continuous variables and Chi-square or Fisher's exact test for categorical variables.

The hospital length of stay after the diagnosis of POI and time to return of bowel function are defined as the interval between the day of POI diagnosis and day of actual discharge from the hospital, and the day of POI diagnosis and day of return of bowel function. T-test will be used to assess differences in the hospital length of stay after diagnosis of POI or time to return of bowel function across treatment groups. Multivariable linear regression will be conducted to adjust for baseline measurements as well as potential confounding variables such as gender, obesity, and operative time. Backwards variable selection will be used with a removal criteria of alpha > 0.1 . When required, data will be transformed in order to meet normality assumptions.

For purposes of statistical analysis, a subset analysis may be done based on history of POI, type of operation, BMI, patients' gender, or other clinically significant co-factors. All data will be analyzed with the use of SAS (version 9.4, The SAS Institute, Cary, NC), SPSS statistical software (SPSS Inc., Chicago, IL), or R version 3.6.1 (www.R-project.org). A p-value <0.05 will be considered statistically significant.

Sample Size Calculations:

We conducted the sample size calculation using estimates of length of stay after the diagnosis of POI . We are assuming equal-sized treatment groups and alpha = 0.05.

We assumed that the average length of stay after the diagnosis of POI in no alvimopan group would be 4.25 days, and alvimopan group 2.75 days. Assuming a log-normal distribution, and co-efficient of variation of 0.6 based on prior data, there will be 80% power to detect decreases of at least 35% in length of stay after the diagnosis of POI in the Alvimopan group relative to the control group with 27 patients in each group, a total of 54 patients. Accounting for a dropout rate of about 5%, our enrollment goal will be 58 patients (29 per group).

Reporting of Results

Aggregate and anonymous, in text and table format, for publication in a medical journal.

Consent

A study coordinator will obtain informed consent from participating patients prior to Alvimopan administration. The coordinator will have HIPPA training, certification in human subject protection, and will be familiar with the research protocol. The study coordinator will explain to each participant the purpose of the study as well as give the patient the opportunity to opt out of participation. Consents will be kept in a room accessible only to qualified research personnel working in the CORS department.

Consents will be obtained prior to alvimopan administration. Patients will be offered participation in the study in a private clinic room. Patients will be offered to participate in the study post-operatively at the time of their post operative ileus diagnosis. Alvimopan is not part of the standard of care. It will be administered free of charge without extra financial charges to the enrolled patients.

References:

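### Does the cost-effectiveness aim in the Background require a cost outcome and a costing method in the plan?

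*Combined protocol and SAP*

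**What the plan says.** The last sentence of the Background opens with "This study aims to evaluate the cost effectiveness of Alvimopan as rescue therapy" and goes on to safety, stay and duration of ileus. The same section gives a price of $142.32 per capsule and a burden figure: "POI has been shown to increase LOS by an average of 6 days with an annual cost of" $1.46 billion.

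The operative sections do not mention cost:

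- **Hypothesis and Objectives:** rescue alvimopan against standard care "in reducing the duration of post-operative ileus and post-operative LOS after colorectal and small bowel resection surgery".
- **Study Design, Outcome:** the primary outcome is stay from ileus diagnosis to discharge. The secondary outcomes are return of bowel function, complications, reoperations and "number of readmissions (any readmissions within 30 days of surgery").
- **Data to be collected:** clinical items, described as information that "is all information already available as part of the patients medical chart". These include "Total number of Alvimopan doses given", stay, nasogastric tube duration, anti-emetics, reoperation and 30-day readmissions. No charge, bill or unit cost is listed.
- **Planned Data Analysis and Sample Size Calculations:** t-tests and linear regression for stay and bowel recovery, and a sample size for stay.
- **Consent:** the drug is free to enrolled patients.

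**The concern.** An aim normally leads to an outcome, a data source and an analysis. Here cost effectiveness is named first in the aim sentence, right after a complaint about the drug's price, and then disappears. Read strictly, the plan sets itself a question that it cannot answer. A cost conclusion in the final report would then rest on unit costs, a time horizon and a rule for readmissions chosen after the data were seen.

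Three further features appear to add to the difficulty:

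- Participation ends 30 days after ileus, while readmissions are counted to 30 days after surgery.
- The outcome definition counts all readmissions, while the follow-up text refers to those caused by the surgery.
- The drug is supplied free, so patient bills might not show it.

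**Working it through.** **1. Does the gap touch the planned inference?** Inputs from Sample Size Calculations: means of 4.25 and 2.75 days, log-normal distribution, coefficient of variation (CV) 0.6, alpha 0.05 (taken as two-sided), 80% power.

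- Log-scale SD = sqrt(ln(1 + 0.6²)) = 0.5545.
- Log ratio = ln(4.25/2.75) = 0.4353.
- Normal approximation: n = 2 × (1.960 + 0.842)² × 0.5545² / 0.4353² = 25.5, so 26 per group. For a decrease of exactly 35%, the log ratio is 0.4308 and n is 27.
- Noncentral t: 27 per group gives 80.8% power for 4.25 against 2.75 days.
- Dropout: 27/0.95 = 28.4, so 29 per group and 58 in total.

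The plan's figures reproduce, and no cost quantity enters them.

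**2. What cost figure can the documents support?** Only drug acquisition. The capsule strength is not given, so one capsule per dose is an assumption.

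| Doses | Drug cost per patient | Break-even cost per bed-day at 4.25 − 2.75 = 1.5 days saved |
|---|---|---|
| 1 | $142.32 | 142.32/1.5 = $94.88 |
| 2 | $284.64 | 284.64/1.5 = $189.76 |
| 3 | $426.96 | 426.96/1.5 = $284.64 |

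No cost per bed-day, reoperation or readmission is stated, so the break-even values cannot be set against a documented cost.

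**3. Can a bed-day cost be recovered from the Background?** Not reliably. Dividing $1.46 billion by 350,000 patients × 6 days × the share affected gives:

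- $695.24 at a share of 100%;
- $1,390.48 at 50%;
- $2,780.95 at 25%.

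The result moves fourfold with a share that is not stated. The text does not say that the three figures describe one population, or that the total is bed-day cost only. The reference cited for the burden is dated 2007, while the capsule price is given as current in a protocol version dated 2021. This range is not fit to prescribe in an analysis.

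**4. Would an added comparison be informative?** With 27 per group and equal means, the 95% half-width of the difference, as a fraction of mean cost, is 1.96 × CV × sqrt(2/27). That is 32.0% at CV 0.6 (the plan's value for stay, borrowed for cost) and 53.3% at an assumed CV of 1.0.

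**5. Do the three supporting points hold?**

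- *Windows.* Put surgery at day 0 and ileus diagnosis at day d, with d > 0. The readmission window closes at day 30. The plan states "Study Completion of participation in the study will be 30 days after the date of POI", which is day 30 + d. The first lies wholly inside the second, so the two clocks are compatible.
- *Readmission wording.* "number of readmissions (any readmissions within 30 days of surgery") and "Any readmission up to 30 days post-operatively to the hospital as a direct result of their surgery will be followed" do differ. The difference belongs to a clinical secondary outcome, and the outcome definition gives analysts the rule to use.
- *Free drug.* No section proposes costing from patient bills. Dose counts are collected, so drug use can be valued directly.

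**The case for a change.** The best case for a change is that the sentence states an aim and is not a passing remark. The Background motivates rescue use by price and notes conflicting earlier findings on cost. Stay cannot simply stand in for cost, because it leaves out the drug's price and readmissions, and the documents never call it a proxy. Deleting a clause is nearly free, whereas leaving it in invites an unplanned cost claim.

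Much of this stands. The mismatch is plain on reading, and the sections concerned show no blacked-out text that could explain it. Any cost figure reported from this trial would be post hoc and should be read that way.

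What does not stand is the step to a needed change. The title, Hypothesis, Objectives, outcomes, analysis and sample size all address effectiveness, and Reporting of Results promises no cost result. The harm therefore depends on the authors later making a claim that the plan does not announce. The fuller remedy, a costing over 30 days from randomisation, would import unit costs from outside the documents. If the readmission outcome were moved to that window while complications and reoperations stayed anchored to surgery, it would also create a new inconsistency.

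**Conclusion.** The inconsistency is real but confined to one clause of the Background, and no change to the plan follows. Removing the clause, or reading cost as the motive for rescue rather than prophylactic use, leaves every outcome, test and sample-size figure as it is. Adding a costing would extend the trial's scope, and its result would depend mainly on a bed-day cost that the documents lack.

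The documented size is a drug cost of $142.32 to $426.96 per treated patient, which at the planned 1.5-day saving is recovered at $94.88 to $284.64 per bed-day. Both ranges assume one capsule per dose and count only drug and bed-days. If the investigators later want a cost comparison, the recorded doses, stay, reoperations and readmissions would support an exploratory one, with unit costs still to be supplied and readmission days or a flat readmission cost still to be settled. The readmission wording is a separate, small point that the outcome definition resolves.

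### Reoperations and complications are counted from surgery rather than from randomisation, and the protocol gives two different scopes for readmissions

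*Combined protocol and SAP*

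**What the plan says.** The Outcome paragraph under Study Design lists three secondary safety outcomes, all timed from the operation: "complications (serious adverse events and adverse events of interest 30 days postoperatively", "number of re-operations (any reoperations within 30 days of surgery" and "number of readmissions (any readmissions within 30 days of surgery".

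The trial starts later for each patient. For eligible patients, "they will be randomized at the time of diagnosis of postoperative ileus". Under inclusion criterion 1b, diagnosis comes after day 5 for open surgery; for the other procedures the condition is "More than 3 days after laparoscopic surgery or ileostomy closure without recovery of GI function". Criterion 1a sets no minimum interval. The Study Completion paragraph ends participation 30 days from the POI date.

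Readmissions are described in three places. The Outcome paragraph puts no restriction on cause. Study Completion follows, to postoperative day 30, only readmissions attributable to the operation. Item 16 of the postoperative data list gives 30 days with neither a start date nor a cause.

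On blinding, the Protocol section states: "The patient and surgical team will be able to know which arm of the study the patient is in". Planned Data Analysis provides frequencies and percentages for categorical variables and names no between-arm test for these three outcomes.

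**The concern.** A randomised comparison of safety should count what happens after allocation. An event before randomisation cannot be caused by the assigned treatment. Yet a reoperation or complication between surgery and POI diagnosis meets the outcome wording. Exclusion 8 (investigator's opinion) may keep some such patients out, but no exclusion names an earlier reoperation or complication.

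The surgery-based window also gives patients different amounts of counted follow-up after randomisation, because the interval from surgery to diagnosis varies.

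The readmission texts raise a separate issue: the same patients can yield two different counts. The narrower count depends on someone judging cause, possibly with knowledge of the arm.

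What is at stake is how the safety results can be read. Safety is a stated aim in the Background, which also mentions reports of more readmissions with alvimopan.

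**Working it through.** **The plan's own figure.** The only design calculation concerns the primary outcome. Inputs from Sample Size Calculations: coefficient of variation 0.6, a 35% decrease, 80% power, alpha 0.05 (taken as two-sided; the plan does not say). On the log scale the variance is ln(1 + 0.6²) = 0.3075 and the difference is -ln(0.65) = 0.4308. Then n = 2 × (1.960 + 0.842)² × 0.3075 / 0.4308², just over 26, rounded up to 27 per group. Allowing for dropout, 27/0.95 = 28.4, rounded up to 29. The plan's figures reproduce, and nothing below alters them.

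**Step 1: weight of one misplaced event.** The plan enrols "a total of 58 patients, 29 in each group". One patient with a pre-randomisation reoperation or complication moves an arm's percentage by 1/29 = 3.4 points. The documents do not say how often this would happen. Readmissions are taken to follow the discharge that ends the POI stay, so this step does not apply to them.

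**Step 2: follow-up inside the window.** Let d be the days from surgery to POI diagnosis. Post-randomisation days counted = 30 - d. Under criterion 1b:
- laparoscopic surgery or ileostomy closure: d > 3, so fewer than 27 days;
- open surgery: d > 5, so fewer than 25 days.

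Under criterion 1a the documents do not bound d.

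**Step 3: late events not counted.** Assume d = 2, 4 or 6 and a constant event rate. For complications and reoperations, risk runs from randomisation and the share counted is (30 - d)/30. For readmissions, risk starts at discharge, so the share is (30 - d - L)/(30 - L), where L is the planned mean stay after diagnosis (4.25 days control, 2.75 days alvimopan).

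| d (assumed) | Days counted | Complications, reoperations | A true 10-point difference appears as | Readmissions, control | Readmissions, alvimopan |
|---|---|---|---|---|---|
| 2 | 28 | 93% | 9.3 | 23.75/25.75 = 92% | 25.25/27.25 = 93% |
| 4 | 26 | 87% | 8.7 | 21.75/25.75 = 84% | 23.25/27.25 = 85% |
| 6 | 24 | 80% | 8.0 | 19.75/25.75 = 77% | 21.25/27.25 = 78% |

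The 10-point column applies to complications and reoperations only. The loss is smaller if events cluster early and larger if they come late.

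**Step 4: comparison with sampling error.** With assumed counts of 3/29 and 6/29, the difference is -10.3 points. SE = √(0.1034 × 0.8966/29 + 0.2069 × 0.7931/29) = 0.0941, so the 95% CI is -28.8 to 8.1 points. The 0.7 to 2.0 points lost in step 3 are small beside that.

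**Step 5: readmission scope.** The Outcome paragraph and Study Completion agree on postoperative day 30 and differ on cause. A readmission judged unrelated to the operation is counted by the first and not followed by the second. Each patient whose readmission status turns on that judgement is again 3.4 points in an arm of 29. The documents give no basis for estimating how many there would be.

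**The case against.** A 30-day postoperative window is a legitimate design choice. POI follows surgery, so participation to 30 days after POI always covers it. A reader might infer that the two time frames contradict each other; they do not, since following patients beyond an outcome window is no error. This stands.

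The interval d is fixed before allocation and balances between arms in expectation. A reader might infer that the window biases the safety comparison; the documents do not support that. This also stands, although balance does not make pre-randomisation events informative about treatment.

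The outcomes could be read as events in enrolled subjects only, because the Consent section places enrolment at POI diagnosis. That reading is open for both reoperations and complications, but the text does not state it, and one sentence would settle it.

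Item 6 of the postoperative list, "Intra-abdominal infection/anastomotic leak", and item 13 (complications, with reoperation) ask for no time or day, unlike items 1, 7 and 8. A reader might infer that event dates will go unrecorded. That does not follow: the list is a set of headings drawn from the chart, and any 30-day window already needs a date.

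Finally, Study Completion may describe only what is followed up, and item 16 has no cause restriction. Even so, the Outcome paragraph would then count readmissions that the follow-up text does not ask anyone to follow.

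**Conclusion.** The point holds as a minor one on secondary safety outcomes. The wording allows a reoperation or complication before randomisation to be credited to an arm, at 3.4 points per patient in an arm of 29. It also leaves 30 - d days of counted follow-up, varying between patients. The bounds of 27 and 25 days follow from criterion 1b; the values at d = 2, 4 and 6, and the loss of late events, rest on assumed intervals and a constant event rate. The effect of the window is noise and some lost late events, without an expected direction.

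The readmission scope is different in kind. Attribution by staff who can know the arm could push the comparison one way. The documents show that possibility, but neither its direction nor its size, so a claim that readmissions will be biased would go too far. The primary outcome is already timed from POI diagnosis; alpha and sample size do not change.

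**What to change.** 1. In the Outcome paragraph, count only complications and reoperations that occur after randomisation. List earlier ones as baseline, placing each by its chart date against the time of ileus diagnosis already collected (postoperative item 1).
2. Use all-cause readmission in the Outcome paragraph, item 16 and Study Completion.
3. Report the three outcomes to 30 days after POI diagnosis, the participation end already stated, alongside the 30-day postoperative rate. Extend readmission follow-up in Study Completion to match. Which rate is the main summary is the sponsor's choice and should be stated in advance.

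The cost is wording, event dates from the chart, and some further chart checks or calls for patients seen before day 30 after POI. Office visits are at roughly 3 to 6 weeks with no stated start. If they spread evenly over days 21 to 42 from surgery (assumption), 9/21 = 43% fall before postoperative day 30, so the present window already needs such checks. The longer one adds d/21 of 58 patients: about 6, 11 and 17 at d = 2, 4 and 6. If the weeks run from discharge at the planned mean stays, the addition is about 6, 11 and 15. Patients may decline the call.

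The change does not remove the gap in post-discharge days between arms (30 - 4.25 = 25.75 control, 30 - 2.75 = 27.25 alvimopan; 1.5 days at the planned means), which comes from the stay itself.

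### Patients enter at different postoperative days after different operations, but the analysis of post-diagnosis stay does not commit to adjusting for surgical approach or postoperative day, and so gives up precision

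*Combined protocol and SAP*

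**What the plan says.** Inclusion Criteria, item 1, lists two ways to meet the definition of postoperative ileus.

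- **1a:** bloating, with or without nausea and vomiting, plus either "Return to NPO status after initial diet attempts" or a nasogastric tube. No postoperative day is given.
- **1b:** no flatus or stool, and either "More than 5 days after open surgery without recovery of GI function" or "More than 3 days after laparoscopic surgery or ileostomy closure without recovery of GI function".

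I read 1a and 1b as alternatives, although the text does not join them with a word. The Protocol section makes early entry under 1a possible: "All patients will follow a standard ERAS pathway after surgery, with early feeding and ambulation". Data item C5 asks "Was there return of bowel function (flatus or stool, solid or liquid, stoma output) prior to ileus", so patients whose bowel had already worked are expected.

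The Outcome paragraph defines the primary outcome as "hospital length of stay after the diagnosis of POI (date of diagnosis until actual discharge". Randomisation takes place at diagnosis, and no stratification factor is stated.

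Planned Data Analysis compares the arms by t-test. It then describes a multivariable linear regression that adjusts for unspecified baseline measurements and "potential confounding variables such as gender, obesity, and operative time", with backward selection removing terms at alpha above 0.1. The regression is not designated as primary. Type of operation appears only among optional subset analyses. The Background raises the possibility that the drug works differently after open and laparoscopic surgery.

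**The concern.** Two patients can start the primary clock at quite different stages of recovery. One may enter under 1a soon after surgery, when early feeding fails. Another may enter under 1b in the second half of the first week or later, after open surgery. Remaining stay plausibly depends on the operation and on how long ago it took place. Both facts are fixed before randomisation, so both are legitimate baseline covariates.

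The plan does not commit to using either. The t-test leaves any such variation in the error term. The regression names three other covariates, and a term added under its open wording could be removed by the selection rule. With 58 patients, prognostic variation left in the error widens the confidence interval. It also lets a chance imbalance in entry day or approach move the estimate more than it needs to.

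**Working it through.** **Inputs from Sample Size Calculations:** means of 4.25 and 2.75 days, a 35% decrease, log-normal stay, coefficient of variation 0.6, alpha 0.05, 80% power, 27 per arm (29 enrolled). Sidedness is not stated; two-sided reproduces the figure.

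**1. The plan's own figure.**
- SD of log stay = sqrt(ln(1 + 0.6²)) = sqrt(0.3075) = 0.5545.
- Effect on the log scale = −ln(0.65) = 0.4308.
- Normal approximation: n = 2 × (1.960 + 0.842)² × 0.3075 / 0.4308² = 26.01, rounded up to 27 per arm. This agrees with the plan.
- Noncentral t power at 27 per arm = 80.0%.

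**2. What fixed adjustment would gain.** If approach and day together explain a share R² of log-stay variance, the residual SD is 0.5545 × sqrt(1 − R²). The power below is for 27 per arm, with two degrees of freedom given up for the two terms.

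| R² (assumed) | Residual SD | Power |
|---|---|---|
| 0 | 0.5545 | 79.9% |
| 0.10 | 0.5261 | 83.9% |
| 0.20 | 0.4960 | 87.9% |

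The first row shows that the terms cost almost nothing if they explain nothing.

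**3. What R² of that size would require.** Take two groups of equal size whose stay differs r-fold (assumption). Then R² = 0.25 × (ln r)² / 0.3075.
- r = 1.3: 5.6%
- r = 1.5: 13.4%
- r = 1.75: 25.5%

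So 10% to 20% corresponds to a contrast on either side of 1.5-fold.

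**4. Chance imbalance.** With 29 per arm and no balancing, the exact binomial probability that the arms differ by 5 or more patients in a given characteristic is 23.7% if half of patients have it, and 19.6% if 30% have it. Both directions are counted. With a 1.5-fold difference in stay, a 5-patient imbalance shifts the log ratio by (5/29) × ln 1.5 = 0.070, or about 7%. The standard error of the log ratio is 0.5545 × sqrt(2/29) = 0.146, so the shift is 0.48 of one standard error.

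**5. Are the variables available?** Procedure and conversion are intraoperative items. The day of diagnosis is item C1, and time of surgery is listed. Item C14 (surgery to discharge) minus item C15 (diagnosis to discharge) also gives the interval from surgery to diagnosis. The qualifying criterion is not a listed data item.

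**The case against.** The strongest reply is that nothing here is broken. Randomisation makes the unadjusted comparison valid whatever the mix of patients. A coefficient of variation taken from prior data may well contain the variation between early and late entrants already, in which case 80% power is right as stated. The interval from the t-test allows for chance imbalance, and the shift in step 4 is under half a standard error. The regression wording is open enough to admit approach and day. The direction is unknown too: late 1b patients could have the more stubborn ileus and the longer stays. All of this stands, and it limits the point to precision. It does not answer why two available baseline variables should be left to discretion and then exposed to removal at alpha above 0.1.

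A reader might go further and infer that early 1a entrants spend much of their stay in ordinary surgical recovery that no ileus drug can shorten, so that the 1.5-day target is out of reach. The documents do not support this. They give no number of non-ileus days for either criterion. The 4.25 days is the mean of the whole control arm, so days assumed for 1a patients cannot be subtracted from it. The Background says stay is mostly set by gastrointestinal recovery, and two of the four discharge criteria concern bowel function and diet. The Background statement that most patients "will experience postoperative ileus, a temporary impairment of gastrointestinal function" does not make 1a entrants ordinary recoverers, because 1a also demands return to NPO or a tube. Item C5 gives no day.

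A reader might also want randomisation stratified by approach and criterion. The criteria overlap: a laparoscopic patient on day 4 with bloating, a tube and no flatus meets both, and no rule assigns that patient. Four strata with small blocks in an open-label trial of 58 would make allocations easier to guess.

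**Conclusion.** The point holds as one of lost efficiency. The criteria admit patients at different postoperative days, the clock starts at diagnosis for all, and the plan leaves approach and postoperative day out of the t-test and uncommitted in the regression. On the assumption that these terms explain 10% to 20% of log-stay variance, power at 27 per arm goes from 80% to about 84% to 88%. The documents contain nothing from which that share can be estimated.

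A reader might infer bias or an underpowered trial. Neither follows. Allocation is random, and the sample size reproduces. Power would fall short only if 0.6 were the variation within groups of similar entrants. For example, a 1-day gap between two equal groups would then give 78.2%, and a 2-day gap 73.0%. The documents do not say that 0.6 has that meaning.

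**What to change.** Amend Planned Data Analysis before any comparison by arm:

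1. Make the primary analysis a linear model of log post-diagnosis stay on treatment, surgical approach (open versus laparoscopic or ileostomy closure) and postoperative day at diagnosis. State that the last two are fixed terms exempt from backward selection. Say how converted operations are classed and how a same-day discharge is counted, since the log needs a positive value.
2. Keep the unadjusted comparison as supportive.
3. Record at entry which criterion was met (1a, 1b or both), and show the primary result by it descriptively.

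The entry criteria and the allocation method need not change for this. The cost is about two degrees of freedom, one tick-box and a few lines of SAP text. If enrolment has begun, the model can still be prespecified from data already being collected. Approach and day will be correlated among 1b patients, because the day threshold depends on approach. That blurs their separate coefficients, which are of no interest here, and does no harm to the treatment estimate.
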